### 5.2.2 Subject Disposition

The number of subjects enrolled and the reasons for screen failure will be summarized. The frequencies of occurrence of completion, discontinuation and each reason for discontinuation of primary and other will be summarized. The data will be described using incidence rate (number of subjects and percentage).

### 5.2.3 Protocol Deviations

The following major protocol deviations will be listed and summarized.

- Recruitment of a subject who did not satisfy the entry criteria
- Excluded medication administered
- Overdose of Investigational Products of 120% or above between two consecutive visits
- Continuation of treatment with investigational product after a treatment related withdrawal event
- IP compliance <80% between two consecutive visits.
- Unauthorized dose adjustment during Core Study
- Missing 2 or more PK samples during the Core Study
- Allowed concomitant AED(s) dose did not remain stable during core phase
- Other clinically relevant deviations to be decided before database lock

## 5.2.4 Demographic and Other Baseline Characteristics

Demographic and other baseline characteristics for the SAS will be summarized using descriptive statistics. Continuous demographic and baseline variables include age, weight, height, and BMI; categorical variables include sex, age group (4-7, 7-12), race and ethnicity.

### **MEDICAL HISTORY**

The number (percentage) of subjects in the SAS reporting a history of any medical condition, as recorded on the CRF, will be summarized. A subject data listing of medical and surgical history will be provided.

Epilepsy-specific medical history for the SAS will be summarized using descriptive statistics, including time since diagnosis, suspected localization of the epileptogenic region and seizure type.

## 5.2.5 Prior and Concomitant Therapy

All investigator terms for medications recorded in the CRF will be coded to an 11-digit code using the World Health Organization Drug Dictionary (WHO DD). Latest Version before database lock will be used for analysis. The number (percentage) of subjects who took prior and concomitant medications will be summarized on the Safety Analysis Set by Anatomical Therapeutic Chemical (ATC) class and WHO DD preferred term (PT). Prior medications will be defined as medications that stopped before the 1st dose of study drug. Concomitant medications will be defined as medications that (1) started before the 1st dose of study drug and were continuing at the time of the 1st dose of study drug, or (2) started on or after the date of the 1st dose of study drug up until 28 days after the subject's last dose. All medications will be presented in subject data listings.

The number of baseline AEDs will be summarized and a summary of baseline and concomitant AEDs will be produced. A baseline AED is an AED taken at Day1. Concomitant AEDs are defined as above for concomitant medications.

Specifically, the number of subjects who take concomitant enzyme inducing antiepileptic drugs (EIAEDs) will be summarized using percentage and frequency.

## 5.2.6 Treatment Compliance

Percent compliance will be calculated for the treatment phase for the FAS as follows:

Compliance

$$= \frac{(\text{Study Med issued in grams} - \text{Study Med Returned in grams})}{(\text{Number of Days} \times \text{Prescribed Daily Dose in ml}) \times \text{Suspension density of 1.07g/ml}} \times 100$$

Overall compliance, each period compliance (Titration (Visit2-Visit6), Maintenance(Visit6-Visit9)) and per visit compliance (Visit2-Visit3, Visit3-Visit4, Visit4-Visit5, Visit5-Visit6, Visit6-Visit7, Visit7-Visit8, Visit8-Visit9) with study medication will be summarized using

descriptive statistics for. Subjects will also be categorized by compliance categories of <80%, 80%-120% and >120%.

### 5.3 Data Analysis General Considerations

#### 5.3.1 Pooling of Centers

Subjects from all centers will be pooled for all analyses.

#### 5.3.2 Adjustments for Covariates

Not applicable.

#### 5.3.3 Multiple Comparisons/Multiplicity

Not applicable.

#### 5.3.4 Examination of Subgroups

The efficacy endpoints will be summarized by disease cohorts (POS, PGTC, and GTC). Within the POS and PGTC disease cohorts, endpoints will also be summarized by age cohort (4 to <7 years,  $\geq 7$  to <12 years), and with or without use of concomitant EIAEDs,

All other endpoints will be summarized by disease cohorts (POS, PGTC, and GTC), age cohort (4 to <7 years,  $\geq 7$  to <12 years), and the presence or absence of concomitant EIAEDs.

#### 5.3.5 Handling of Missing Data, Dropouts, and Outliers

##### 5.3.5.1 Efficacy

For the last observation carried forward (LOCF) analyses, such as “Maintenance-LOCF” analyses of responder rate, if the overall duration of the Maintenance Period is less than 8 weeks, the diary data up to the last 8 weeks during the Titration and Maintenance Periods combined will be used to calculate the seizure frequency per 28 days for Maintenance-LOCF.

Since data is rank transformed prior to analysis, outliers will have no effect on the calculation for confidence interval of percent change in seizure frequency per 28 days.

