9.7.1.1.2 SECONDARY ENDPOINTS

The following endpoints will be analyzed:

1. The relationship between plasma levels of perampanel and efficacy endpoints (ie, change in average seizure frequency over 28 days, responder probability, and the proportion of subjects who are seizure-free in the Maintenance Period of the Core Study) separately for each seizure type
2. The relationship between plasma levels of perampanel and cognition endpoints including change from baseline in ABNAS, CBCL, and LGPT. In addition, depending

on the AE data, the relationship between plasma levels of perampanel and select AEs will be assessed.

3. Change from baseline at Week 23 and Week 52 in ABNAS, CBCL, and LGPT
4. Changes from baseline at Week 23 and Week 52 in growth and development parameters (height, weight, thyroid, and IGF-1)
5. Change from baseline in EEG and the frequency of EEG abnormalities during awake and sleep state
6. Proportion of subjects (aged 6 or older at time of consent/assent) with any treatment-emergent reports of suicidal ideation and behavior on the C-SSRS and intensity of these behaviors assessed using C-SSRS scores
7. The median percent change in seizure frequency per 28 days during Treatment Phase (Titration Period and Maintenance Period) of the Core Study, and during the long-term treatment (up to 52 weeks) relative to the Pretreatment Phase. Seizure frequency will be based on the number of seizures per 28 days, calculated as the number of seizures over the entire time interval divided by the number of days in the interval and multiplied by 28.
8. Proportion of responders (25% responders defined as a decrease in 28-day seizure frequency of equal or greater than 25% compared to baseline seizure frequency; 50% responders defined as a decrease in 28-day seizure frequency of equal or greater than 50% compared to baseline seizure frequency; 75% responders defined as a decrease in 28-day seizure frequency of equal or greater than 75% compared to baseline seizure frequency) during Maintenance Period of Core Study, and during the long term treatment (up to 52 weeks)
9. Proportion of subjects who are seizure-free during Maintenance Period of Core Study, and during the long-term treatment (up to 52 weeks)
10. CGI of Change

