#### 5.1.2 Secondary Endpoints

The following endpoints will be analyzed:

1. The relationship between plasma levels of perampanel and efficacy endpoints (ie, change in average seizure frequency over 28 days, responder probability, and the proportion of subjects who are seizure-free in the Maintenance Period of the Core Study) separately for each seizure type
2. The relationship between plasma levels of perampanel and cognition endpoints including change from baselines in ABNAS, CBCL, and LGPT. In addition, depending on the AE data, the relationship between plasma levels of perampanel and select AEs will be assessed
3. Change from baseline at Week 23 and Week 52 in ABNAS, CBCL, and LGPT
4. Changes from baseline at Week 23 and Week 52 in growth and development parameters (height, weight, thyroid, and IGF-1)
5. Change from baseline in EEG and the frequency of EEG abnormalities during awake and sleep state
6. Proportion of subjects (aged 6 or older at time of consent/assent) with any treatment-emergent reports of suicidal ideation and behavior on the C-SSRS and intensity of these behaviors assessed using C-SSRS scores
7. The median percent change in seizure frequency per 28 days during Treatment Phase (Titration Period and Maintenance Period) of the Core Study, and during the long-term treatment (up to 52 weeks) relative to the Pretreatment Phase. Seizure frequency will be based on the number of seizures per 28 days, calculated as the number of seizures over the entire time interval divided by the number of days in the interval and multiplied by 28
8. Proportion of responders (25% responders defined as a decrease in 28-day seizure frequency of equal or greater than 25% compared to baseline seizure frequency; 50% responders defined as a decrease in 28-day seizure frequency of equal or greater than 50% compared to baseline seizure frequency; 75% responders defined as a decrease in 28-day seizure frequency of equal or greater than 75% compared to baseline seizure frequency) during Maintenance Period of Core Study, and during the long term treatment (up to 52 weeks)
9. Proportion of subjects who are seizure-free during Maintenance Period of Core Study, and during the long-term treatment (up to 52 weeks)
10. CGI of Change

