## 5.2 Study Subjects

### 5.2.1 Definitions of Analysis Sets

The **Safety Analysis Set (SAS)** is the group of subjects who received at least 1 dose of study drug and had at least 1 postdose safety assessment.

The **Full Analysis Set (FAS)** is the group of subjects who received at least 1 dose of study drug and had at least 1 postdose primary efficacy measurement.

**PK Analysis Set** is the group of subjects receiving perampanel and with at least 1 quantifiable perampanel concentration at one of the visits during the Maintenance Period of the Core Study and with adequately documented dosing history.

**PK/PD Analysis Set** is the group of subjects receiving perampanel who have seizure frequency, cognition, or AE data with documented dosing history. Subjects receiving perampanel should have at least 1 quantifiable perampanel concentration at one of the visits during the Maintenance Period of the Core Study as per the PK Analysis Set.

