## 5.4 Efficacy Analyses

Only “valid days” and “valid seizure counts” will be used in the calculations of seizure frequency per 28 days. A “valid day” is defined as the day where seizure counts information is present, that is, either a record with an answer of ‘No’ to the question ‘Did the subject experience any seizures?’ or a positive number of seizures for at least one of the seizure types collected. “Valid seizure counts” are the seizure counts that are read from the valid seizure days.

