### 5.4.2 Secondary Efficacy Analyses

The percent change in seizure frequency per 28 days during Treatment Phase (Titration Period and Maintenance Period) of the Core Study with respect to during the Pretreatment Phase will be summarized using descriptive statistics (n, mean, median, minimum, maximum and 95% confidence interval). The percent change in seizure frequency per 28 days are calculated for Total seizure, POS total seizure and total complex partial seizure for POS cohort, for PGTC seizure, absence seizure, myoclonic seizure and total seizure for PGTC cohort and for Secondarily Generalized seizures for GTC cohort. Total Seizures is sum of all seizures, including POS, generalized and other seizures. Total POS Seizures is sum of all POS seizures, including simple partial seizures without motor signs, simple partial seizures

with motor signs, complex partial seizures and complex partial seizures with secondary generalization. Secondly Generalized seizures cohort is a subset of the POS cohort. The proportion of subjects who are seizure-free and the proportion of responders based on decrease from baseline (during the Pretreatment Phase) in 28-day seizure frequency of equal or greater than 25%, equal or greater than 50%, and equal or greater than 75% during Maintenance-LOCF Period of the Core Study will be summarized using frequency count (number and percentage). If subjects complete the Core study and have no seizure during the Maintenance Period, those will be treated as seizure-free.

The number of subjects with new seizure types compared to Baseline Period and Seizure history will be counted.

For analysis for the Japanese submission, all of analysis will be conducted for Japanese population but the following analysis also will be conducted.

The percent change in seizure frequency of POS total seizure per 28 days during Treatment Phase (Titration Period and Maintenance Period) of the Core Study with respect to the Pretreatment Phase will be summarized using descriptive statistics (n, mean, median, minimum, maximum and 95% confidence interval) by 4 week periods (1-4week, 5-8week, 9-12 week, 13-16 week, 17-20 week, 21-23 week, last 4 weeks of treatment).

The CGI-I and CGI-S will be summarized for each visit using frequency count (number and percentage).

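### Maintenance-LOCF has no minimum diary length, so a child who stops within days in Titration can be counted as a Maintenance responder

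*SAP*

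**What the plan says.** The responder endpoint in Protocol 9.7.1.1.2 (item 8) is measured "during Maintenance Period of Core Study, and during the long term treatment (up to 52 weeks"). Core SAP 5.1.2 repeats it, with "50% responders defined as a decrease in 28-day seizure frequency of equal or greater than 50% compared to baseline seizure frequency".

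Core SAP 5.4.2 then tabulates response at 25%, 50% and "equal or greater than 75% during Maintenance-LOCF Period of the Core Study". Section 5.3.5.1 defines that period. The rule applies "if the overall duration of the Maintenance Period is less than 8 weeks". In that case "the diary data up to the last 8 weeks during the Titration and Maintenance Periods combined will be used to calculate the seizure frequency", scaled to a 28-day rate.

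Three other provisions bear on the point:

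- Core SAP 5.2.1 admits a treated child to the Full Analysis Set who "had at least 1 postdose primary efficacy measurement".
- Core SAP 5.4 says a valid day "is defined as the day where seizure counts information is present". It does not say how many valid days are needed.
- For seizure freedom, Core SAP 5.4.2 says: "If subjects complete the Core study and have no seizure during the Maintenance Period, those will be treated as seizure-free".

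**The concern.** A child who stops during Titration has zero weeks of Maintenance. Zero is less than 8, so on its plain reading the rule applies and the child is rated on whatever on-drug diary exists. If the drug is stopped on Day 7 for intolerance and no seizure was recorded that week, the frequency is 0 per 28 days and the change is -100%. That child enters the table as a 25%, 50% and 75% responder for an endpoint named after a period the child never reached.

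A short window makes an empty or near-empty diary likely by chance alone. The study has one arm, so there is no control group in which the same artefact would appear. No observed-case or non-responder version of the responder rate is planned, so the reported table would not show how much of it comes from such children.

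**Working it through.** The documents give no responder rate, dropout rate or power for this endpoint, so there is no stated figure to reproduce. The 65-subject, 80% power statement in Core SAP 4 concerns the confidence interval for median percent change in Japan.

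**1. Chance response with no drug effect**

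Inputs from the documents:

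- The 50% threshold (Core SAP 5.1.2).
- A window of up to 56 days (5.3.5.1), with Maintenance up to 84 days (3.2).
- Baseline taken from all pre-dose diary (8.1.1).
- Entry on as little as one seizure in 12 weeks, or 4 weeks in Japan (Protocol 9.3.1), so low rates are eligible.

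Assumptions: Poisson counts; a 28-day baseline with at least one seizure (percent change is undefined otherwise); an unchanged true rate r per 28 days. Shorter baselines, allowed outside Japan, are not modelled.

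Formula: B ~ Poisson(r) given B ≥ 1, and T ~ Poisson(r·d/28) over d diary days. The child responds if T·28/d ≤ 0.5·B.

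Hand check at r = 4, d = 7, where T has mean 4 × 7/28 = 1:

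- T = 0 always responds: e^-1 = 0.368.
- T = 1 scales to 4 per 28 days, so it needs B ≥ 8. That has probability 0.052 given B ≥ 1, and 0.368 × 0.052 = 0.019.
- T = 2 needs B ≥ 16, which is negligible.
- The sum is 0.387. Simulation with 400,000 draws also gives 0.387.

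Simulated chance of a 50% response:

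| Seizures per 28 days | 7 days | 14 days | 28 days | 56 days | 84 days |
|---|---|---|---|---|---|
| 1 | 78% | 62% | 53% | 54% | 41% |
| 2 | 61% | 43% | 37% | 31% | 22% |
| 4 | 39% | 31% | 22% | 16% | 11% |
| 8 | 29% | 19% | 11% | 6% | 3.5% |
| 30 | 9% | 3% | 0.6% | 0.1% | about 0% |

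The 75% threshold is more sensitive: 61% at 7 days against 5% at 84 days for r = 2, and 37% against 0.6% for r = 4.

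Overdispersion weakens the contrast at high rates. With a negative binomial (k = 1) and the baseline fixed at its true rate, the 50% response chance at 7 against 84 days is 80% against 44% at r = 1, but 39% against 40% at r = 30.

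**2. Effect on the reported rate**

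Let D be the share who stop early, p the responder rate in the others, and q the chance that a stopper scores as a responder. Then the LOCF rate is (1 − D)·p + D·q, and the rate counting stoppers as non-responders is (1 − D)·p. The difference is D·q, which cannot be negative.

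Illustration with assumed D = 10%, p = 40%, and every stopper having 7 diary days and no drug effect. Here q is the simple Poisson value with baseline fixed at r. The non-responder rate is 0.9 × 40% = 36.0%.

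| Seizures per 28 days | q | LOCF rate | Against non-responder counting | Against the 40% in those who stayed |
|---|---|---|---|---|
| 1 | 77.9% | 36.0 + 7.8 = 43.8% | +7.8 points | +3.8 points |
| 4 | 36.8% | 36.0 + 3.7 = 39.7% | +3.7 points | -0.3 points |
| 30 | 5.9% | 36.0 + 0.6 = 36.6% | +0.6 points | -3.4 points |

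Over D = 5% to 20%, the excess over non-responder counting is 3.9 to 15.6 points at 1 seizure per 28 days, 1.8 to 7.4 at 4, and 0.3 to 1.2 at 30. These use 7-day diaries throughout, which is close to the worst case.

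**The case against.** The best defence is that some rule is needed. Protocol 9.7.1.6 summarises responders in the Full Analysis Set, which includes children with no Maintenance data, and Protocol 9.7.1 leaves detail to the SAP. A missing-data convention that fills this gap is legitimate. That stands, and it is why the remedy keeps Maintenance-LOCF.

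It is also fair that the Day-7 case is an extreme. A child treated for 8 weeks or more contributes a full 56-day window with complete diaries, where the chance figures are much closer to those for 84 days. Nor does any success decision rest on the responder rate: the primary endpoint is safety, Core SAP 5.4.1 lists no primary efficacy analysis, and the Japan criterion uses median percent change over the whole Treatment Phase. These facts limit the weight of the point but do not supply the missing floor.

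Three stronger readings are tempting and are not supported:

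- **That early dropouts do inflate the responder rates.** This is certain only against non-responder counting, where it follows by construction. Against the children who stayed, the sign changes with baseline frequency.
- **That the SAP changed the protocol endpoint without disclosing it.** Core SAP 7 logs only changes made after SAP version 2.0, and that version is not in the documents. The absence of an entry shows nothing.
- **That the completion rule for seizure freedom contradicts the responder rule.** One is an absolute state over a period and the other a rate, so different dropout rules can coexist. The contrast only shows that the plan could set a data requirement where it wanted one.

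**Conclusion.** The gap is real and narrow. As written, Core SAP 5.3.5.1 allows a few days of Titration diary to produce a Maintenance responder, and no planned table would reveal it. A 7-day diary roughly doubles the chance of a spurious 50% response relative to the full 56-day window at 2 seizures per 28 days (61% against 31%), and multiplies it by nearly five at 8 (29% against 6%).

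Its contribution to the overall rate is greatest where baseline frequency is low and stopping is early. The net size cannot be stated, because dropout, its timing and the baseline distribution are not in the documents. The chance figures assume Poisson counts and no drug effect.

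Only the Core 25%, 50% and 75% responder rates are affected, and these are secondary and descriptive. Percent change and the Japan criterion do not use Maintenance-LOCF, and seizure freedom is protected provided the Core-completion rule in 5.4.2 governs it. The change should be made, but the trial's main conclusions do not depend on it.

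**What to change.** In Core SAP 5.3.5.1 and 5.4.2:

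- State a minimum number of valid diary days for Maintenance-LOCF responder status, for example 28, and count treated children below it as non-responders. This also covers diaries that are short because entries are missing. At 28 days the chance of a 50% response falls to 37%, 22% and 11% at 2, 4 and 8 seizures per 28 days, so the floor limits the problem without removing it.
- Add one sensitivity table that counts children who stopped study drug before 8 weeks of Maintenance as non-responders. It should be a sensitivity analysis and not the main table, because it errs the other way: a child who responds through 11 weeks of Titration and 7 of Maintenance and then stops would be scored as a failure.
- Report how many Maintenance-LOCF responders never entered Maintenance.

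The cost is a few lines of SAP text, one more table, and a slightly less favourable responder rate.

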##### 5.3.5.2 Safety

The algorithm on the assumptions used for imputing the missing dates for AEs is given in the programming specifications.

If the day and month are missing, events will be considered treatment-emergent if the year is equal to or after the year of the first dose date; if days are missing, events will be considered treatment-emergent if the year is after the year of the first dose, or if the year is equal to the year of the first dose date and the month is equal to or after the month of the first dose date.

For the purpose of summarizing maximum severity, if the severity of an adverse event (AE) is missing for a subject, then, if this subject has another AE with the same preferred term that has “severe” severity, the maximum severity of the AE will be noted as “severe”; otherwise the maximum severity will be noted as missing. Similarly, for the purpose of summarizing closest relationship, if the relationship of an AE to study drug is missing, the AE will be noted to be probably related if there is another probably related AE with the same preferred term, otherwise this relationship will be noted as missing.

For determining treatment emergent markedly abnormal lab values, a missing baseline lab value will be assumed to be of grade 0.

The algorithm to impute missing dates for concomitant medications is given in the programming specifications. No special handling of missing data is planned for the analysis of any of the other safety variables.

Data exceptions or outliers will be determined by inspection of the tables, listings, and graphs in consultation with the clinical study team. The effect of outliers on analyses may be assessed by re-analyzing the data without the outliers.

All the listings will display the original missing values.

